2.4.2 Prior, concomitant and post therapies

Missing or partially missing start/end dates for prior/concomitant therapies will be imputed using the Novartis ADaM Governance Board (AGB) global standard approach.

Prior and concomitant medications/non-drug therapies will be identified based on recorded or imputed start and end dates. Details will be provided in the study programming datasets specifications (PDS).

Prior medications are defined as any recorded medication with its start date (recorded or imputed) prior to the date of the first dose of the study drug. Concomitant medications are defined as any recorded medication with its end date (recorded or imputed) later than or equal to the date of the first dose of the study drug and start date (recorded or imputed) prior to or equal to the end date of the treatment period.

Prior non-drug therapies are defined as any procedure/significant non-drug therapy with its start date (recorded or imputed) prior to the date of the first dose of the study drug.

Concomitant non-drug therapies are defined as any recorded procedure/significant non-drug therapy with its end date (recorded or imputed) later than or equal to the date of the first dose of the study drug and start date (recorded or imputed) prior to or equal to the end date of the treatment period. Whereas patients who undergo heart transplant will also be listed for the treatment period and the study period together.

Concomitant medications and significant non-drug therapies prior to and after the start of the study treatment will be summarized by anatomical therapeutic classification (ATC 3) and preferred term, for overall and for each age group.

Concomitant heart failure medications (including ACE-inhibitors, ARBs, renin inhibitors, beta-blockers, calcium antagonists, diuretics, aldosterone antagonists, cardiac glycocytes, aspirin, oral anticoagulants, antiarrhythmics agents, nitrates) will be summarized by ATC and preferred term, for overall and for each age group.

The SAF will be used for the above analyses.

2.5 Analysis of the primary objective

The primary objective is to evaluate safety and tolerability of LCZ696 in eligible heart failure patients from PANORAMA-HF receiving open-label investigational drug.

2.5.1 Primary endpoint

Adverse events, laboratory assessments, vital signs, and duration of drug exposure are considered primary endpoints.

2.5.2 Statistical hypothesis, model, and method of analysis

Refer to [Section 2.8.1](#), [Section 2.8.2](#), [Section 2.8.3](#) and [Section 2.8.4](#).

2.5.3 Handling of missing values/censoring/discontinuations

Refer to [Section 2.8.1](#), [Section 2.8.2](#), [Section 2.8.3](#) and [Section 2.8.4](#).

2.5.4 Supportive analyses

Not applicable, there are no supportive analyses.

2.6 Analysis of the key secondary objective

Not applicable, there is no key secondary objective.

2.7 Analysis of secondary efficacy objective(s)

Not applicable, there are no secondary objectives.

2.8 Safety analyses

The SAF will be used for all safety analyses, unless specified otherwise.

2.8.1 Adverse events (AEs)

All AEs will be identified using Medical Dictionary for Regulatory Activities (MedDRA). The MedDRA version used for reporting the study will be described in a footnote.

An AE with its severity increased should be considered and recorded as a new AE.

Treatment emergent adverse events (TEAEs) are defined as any recorded AE with its start date-time (recorded or imputed) on or after the start date-time of the treatment period and end date as the end date of the treatment period or the date of last dose taken as reported in the DAR page + 30 days. Any AE happening after treatment discontinuation +30 days but still within the study period (e.g., where patient did not discontinue the study on the same date of treatment discontinuation) would not be considered as a TEAE and will be reported in the listing of AE.

The following adverse events will be summarized by primary system organ class, preferred term, and maximum severity as appropriate, for each age group and for overall, using numbers and percentages of patients with at least one adverse event in the corresponding class (see list below). Outputs will be produced for AEs regardless of study-drug relationship, and for study-drug related AEs. Study drug related AEs are defined as any recorded AE with “Reasonable possibility that AE is related to study treatment” answered as “YES”. Serious adverse events (SAEs) are defined as any recorded AE with “Does AE meet the definition of an SAE” answered as “Yes”.

Adverse events summaries

- Any adverse event (treatment emergent or not)
- Any serious adverse event (treatment emergent or not)
- Treatment emergent adverse event (TEAE)
- Treatment emergent serious adverse event
- Treatment emergent adverse event (TEAE) occurred in >5% of patients
- Treatment emergent serious adverse event (TESAE) occurred in >5% of patients

- Treatment emergent adverse event of special interest, e.g. angioedema (both, adjudicated and non-adjudicated), change in bone growth and density, cognitive impairment (narrow SMQ), embryo-fetal toxicity or lethality, hepatotoxicity, hyperkalemia, hypersensitivity, hypotension, malignancy, neonatal or infantile toxicity through exposure from breast milk, renal impairment (narrow SMQ), and/or statin drug interaction as defined in the Case Retrieval Sheet for LCZ696 (see [Section 2.8.1.1](#))
- TEAE and TESAE leading to dose adjustment, temporary dose interruption, or permanent discontinuation (including death) of study treatment
- TEAE and TESAE leading to permanent discontinuation (including death) of study treatment
- TEAE and TESAE leading to death

The following rules are applicable to the summaries:

- If a patient reported more than one AE with the same PT, the patient will be counted only once with the greatest severity at the PT level
- If a patient reported more than one AE within the same SOC, the patient will be counted only once with the greatest severity at the SOC level, where applicable.

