If monthly home urine pregnancy tests are utilized, child-bearing potential female subjects will be given a urine pregnancy test kit for each month between study visits and will be instructed to perform a urine pregnancy test at home, once per month (approximately every 30 days). Subjects will be given a Pregnancy Test Diary in which they are to record the date and the results of their pregnancy tests that are done at home, each time they run the test. Where possible, Study Site personnel will contact the subject on a monthly basis to check that the subject has completed the urine pregnancy test and has recorded the result in the Pregnancy Test Diary. The Study Site personnel may also ask for the result of the pregnancy test. The contact by the Study Site personnel and the result of the pregnancy test will be documented in the source documentation for the subject. The Pregnancy Test Diary will be part of the source documentation for the subject. If the pregnancy test is positive, the subject/parents/guardian must contact the investigator immediately. The aforementioned pregnancy testing (i.e. done at home or at the study site) will be maintained during treatment and until the end of relevant systemic exposure.

All menarchal girls and their parents/caregivers should be informed about the potential risks of pregnancy and the need to prevent pregnancy during the study. It is important to be sensitive in introducing this issue, as understanding and comprehension of puberty, sexual activity, pregnancy and contraception is influenced by age; as well as, factors such as precocity, socio-educational economic and familial background. These discussions are therefore best performed by investigators familiar with the pediatric subject and her family and should be guided by requirements of the local regulatory authorities. These discussions should take into account the socio-economic, cultural factors and religious beliefs of the adolescent participant and her family. The investigator should also discuss the management of the pregnancy test results with the subject and her parents/caregivers. The privacy of the subject should be considered in accordance with the local law and ethics.

Any subject with a positive pregnancy test must discontinue study drug immediately, should be discontinued from the study, and should be seen at the site for Visit 599 .

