#### **10.1.4 Pregnancy reporting**

##### **Pregnancies**

Should a pregnancy be discovered during the course of study, the following procedure must be followed. In case of pregnancy discovered during the screening period, the patient will be withdrawn from the study immediately.

To ensure patient safety, each pregnancy occurring after signing the informed consent must be reported to Novartis within 24 hours of learning of its occurrence. The pregnancy should be followed up to determine outcome, including spontaneous or voluntary termination, details of the birth, and the presence or absence of any birth defects, congenital abnormalities, or maternal and/or newborn complications.

Pregnancy should be recorded and reported by the investigator to the Novartis Chief Medical Office and Patient Safety (CMO&PS). Pregnancy follow-up should be recorded on the same form and should include an assessment of the possible relationship to study treatment any pregnancy outcome.

Any SAE experienced during the pregnancy and unrelated to the pregnancy must be reported on a SAE form.

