2.8.1.1 Adverse events of special interest / grouping of AEs

Most common TEAEs are defined as any recorded TEAE corresponding to a PT with at least 5% of patients having at least one TEAE of this PT. Most common TEAEs will be derived overall and by age group and will be summarized by age group and for overall, by SOC and PT, in descending frequency according to incidence, starting from the most common event.

[Table 2-1](#) shows the identified and potential risks for LCZ696 and the specifically specified analyses for each risk. In addition, the following standard analyses will be applied to all risks.

- Numbers and percentages of patients with any TEAE within the risk category (or SOC/PT within risk category) by age group and risk category, SOC, PT and maximum severity.
- Exposure adjusted incidence rates per 100 patient-years for TEAEs within the risk category by age group and risk category.
- Listing of patient numbers per risk.

Table 2-3 Identified and potential risks

Risk	Analysis
Hyperkalemia	1. Standard analyses; 2. Numbers and percentages of patients with treatment emergent hyperkalemia among patients with/without hyperkalemia at baseline by age group and overall 3. Numbers and percentages of patients with any post-baseline serum potassium ≥ 5.5 mEq/L, >6.0 mEq/L and >6.5 mEq/L by age group and overall
Hypotension	1. Standard analyses;

Risk	Analysis
	
2. Blood pressures and change from baseline in blood pressures will be summarized by visit, time point, age group and overall using number of observations, mean, standard deviation, median, minimum, Q1, Q3, and maximum;
 
3. Numbers and percentages of patients with the following events during the treatment period will be provided by age group and overall:
 
• Post-baseline systolic blood pressure (SBP) < 5th percentile per age (Table 16-7 in the protocol);• At least 20 mmHg drop in SBP (post-baseline assessments comparing to baseline);• Simultaneous treatment emergent symptomatic hypotension and postbaseline SBP < 5th percentile per age (Table 16-7 in the protocol);• Simultaneous treatment emergent symptomatic hypotension and at least 20 mmHg drop in SBP (post-baseline assessments comparing to baseline);• Simultaneous post-baseline SBP < 5th percentile per age (Table 16-7 in the protocol) and at least 20 mmHg drop in SBP (post-baseline assessments comparing to baseline).
Angioedema (positively adjudicated events)	Standard analyses;

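### Embryo-fetal toxicity is counted only as a treatment-emergent event, so harm first seen at a term birth falls months outside the window, and no SAP output uses the pregnancy follow-up that the protocol requires

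*SAP*

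**What the plan says.** **Topic and counting rule.** SAP 2.8.1 gives the treatment-emergent events of special interest, which include "embryo-fetal toxicity or lethality, hepatotoxicity, hyperkalemia, hypersensitivity, hypotension, malignancy, neonatal or infantile toxicity through exposure from breast milk". The terms behind each topic are in the Case Retrieval Sheet, which is not part of the documents. SAP 2.8.1.1 applies standard analyses to every topic in that sheet. The first is "Numbers and percentages of patients with any TEAE within the risk category" and the second is an exposure-adjusted rate per 100 patient-years, also restricted to TEAEs and given by age group.

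**Window.** A TEAE starts on or after the start of treatment, with "end date as the end date of the treatment period or the date of last dose taken as reported in the DAR page + 30 days". For later events, SAP 2.8.1 says: "Any AE happening after treatment discontinuation +30 days but still within the study period" (for example, where treatment stopped before study exit) "would not be considered as a TEAE and will be reported in the listing of AE". SAP 2.1.1 ends the study period at Visit 599.

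**Pregnancy.** Protocol 8.4.2 requires monthly urine tests and says: "Any subject with a positive pregnancy test must discontinue study drug immediately, should be discontinued from the study, and should be seen at the site". The visit meant is Visit 599. Protocol 10.1.4 then says: "The pregnancy should be followed up to determine outcome, including spontaneous or voluntary termination, details of the birth, and the presence or absence of any". That sentence goes on to name anomalies in the child and complications in mother or newborn. This goes to the sponsor's patient safety department.

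**Other outputs.** SAP 2.8.1 also plans summaries that are not limited to TEAEs, among them "Any serious adverse event (treatment emergent or not"). SAP 2.8.4 covers vital signs and growth. No SAP section lists or summarises pregnancies or their outcomes, although Protocol 8.4 names pregnancy as a safety evaluation.

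**The concern.** A 30-day tail after the last dose suits events that follow exposure closely. Embryo-fetal harm is different: exposure ends when the pregnancy is detected, but an anomaly, a stillbirth or a newborn complication may be first recorded only at or near delivery. The rule that stops the drug therefore starts a 30-day clock that expires long before a term delivery.

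The SAP names this risk and will print a row for it. A zero or low count there, and a matching rate per 100 patient-years, could be read as evidence about birth outcomes that the row was not built to see. The denominator adds to this. The rate is given by age group, one of which is 1 to under 6 years, and the SAP states no restriction to females of childbearing potential or to exposed pregnancies.

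**Working it through.** The plan has no figure to reproduce here: the study is descriptive and single-arm, with no required sample size. The check is a comparison of dates, counted in days from conception.

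**Inputs from the documents**
- Pregnancy tests about every 30 days, and at all in-person visits (Protocol 8.4.2); in-person visits every 6 months after titration (Protocol 8).
- Drug stopped at once on a positive test (Protocol 8.4.2).
- TEAE window to last dose + 30 days (SAP 2.8.1). The SAP joins two end points with *or*. I take last dose + 30 days as the later one, assuming that treatment disposition is dated at the stop.

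**Assumptions not in the documents**
- A test turns positive on day p = 14 (range 10 to 21).
- The next test comes d days later, with d from 0 to 30 under monthly testing.
- Gestational age runs from 14 days before conception, so birth at G weeks falls on day 7G − 14: 24 weeks = day 154, 37 weeks = day 245, 40 weeks = day 266.

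**Formulas**
- Drug stop = p + d
- Window close = p + d + 30
- Gap = (7G − 14) − (p + d + 30)

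| Case | p | d | Drug stop | Window close | Gap, 24 wk | Gap, 37 wk | Gap, 40 wk |
|---|---|---|---|---|---|---|---|
| Earliest | 10 | 0 | 10 | 40 | 114 | 205 | 226 |
| Central p, full delay | 14 | 30 | 44 | 74 | 80 | 171 | 192 |
| Latest, monthly tests | 21 | 30 | 51 | 81 | 73 | 164 | 185 |

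Under monthly testing the window thus closes at (40 + 14)/7 = 7.7 to (81 + 14)/7 = 13.6 weeks' gestation. A loss before then can count. A 40-week birth falls 185 to 226 days after it, and even a 24-week birth falls 73 to 114 days after it.

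**Stress test.** Suppose that only the 6-monthly site tests are done and the delay is the full 183 days. The window then closes on days 223 to 234. A 40-week birth still falls 32 to 43 days outside and a 37-week birth 11 to 22 days outside, but births at 24 or 28 weeks no longer fall after the close. For a 40-week birth to fall inside, drug must still be taken on day 266 − 30 = 236. With p = 14 that means (236 − 14)/30 = 7.4, or about 7 monthly tests missed.

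**Do the wider tables catch it?** Protocol 10.1.1 requires AE monitoring for at least 30 days after the last dose. Protocol 10.1.3 requires every SAE to be reported until 30 days after the last visit, and after that only if the investigator suspects causality. If Visit 599 takes place v days after the stop, unconditional SAE reporting closes v days later than the TEAE window. For a 40-week birth under monthly testing, v would have to be at least 185 days, whereas Protocol 8 asks for the final visit as soon as possible. Capture in the wider tables is therefore possible but not assured.

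**The case against.** The strongest reply is that nothing is lost to safety monitoring. Protocol 10.1.4 requires each pregnancy to be reported within 24 hours, followed to outcome and assessed for relationship to treatment. A newborn is not in the Safety Set, so keeping offspring outcomes out of patient-level AE tables is a coherent structure, and where to report them is partly preference. Contraception is required and pregnancies are probably few. All of this stands, and it is why the point is minor. It does not explain why the SAP gives the risk a row and a rate whose counting rule leaves out term outcomes, without saying so.

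Four stronger readings are tempting, and the documents do not support them:

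- *The row must be zero.* Early losses inside the window count, and so might a pregnancy that goes undetected for long. The Case Retrieval Sheet terms and the way such events are dated are not supplied, so the exact content of the row is unknown.
- *The breast-milk topic has the same defect.* That topic is lactation exposure, not harm seen at birth. Nursing women are excluded (Protocol 5.2) and pregnant subjects leave the study off drug, so it is near-empty by eligibility, not because of the window.
- *A late outcome cannot appear anywhere in the SAP outputs.* The all-AE and all-SAE summaries are not limited to TEAEs, and a congenital anomaly is a seriousness criterion (Protocol 10.1.2). A late event could appear if it were entered. The accurate statement is that capture is not assured.
- *The outcome is never collected.* It is; the gap is in SAP reporting.

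**Conclusion.** The point holds for the embryo-fetal topic alone. Under the stated TEAE rule and an immediate stop at a positive test, harm first seen at a term birth falls outside the planned counts and rates: by about 185 to 226 days for a 40-week birth and 164 to 205 days for a 37-week birth. These ranges assume that monthly tests are done and that a test turns positive 10 to 21 days after conception. With only 6-monthly tests the margin for term births shrinks to weeks but remains. The birth outcomes that the protocol requires to be followed have no planned SAP output.

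The consequence is a risk of misreading a zero or low row, not a demonstrated error in a result. Neither the number of pregnancies nor the number of females of childbearing potential is given, so the effect cannot be expressed in patients. This is a minor but worthwhile correction to the SAP.

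**What to change.** In SAP 2.8.1.1:

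1. Add a listing of all pregnancies exposed to study drug, taken from the Protocol 10.1.4 follow-up regardless of the TEAE window and the study period. For each, show the timing of exposure and the outcome: live birth, loss, termination, anomaly or newborn complication, or pending or unknown at database lock. State the total number of exposed pregnancies.
2. Drop the per-100-patient-year TEAE rate for embryo-fetal toxicity, or footnote the row to say that it cannot capture birth outcomes and refer to the listing.

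The cost is a paragraph of SAP text and one short listing, reconciled with follow-up that the protocol already requires. The downside is that some outcomes may still be pending at lock and must be shown as such. No new data collection is needed, and no clinical or stopping rule changes.

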2.8.1.1 Adverse events of special interest / grouping of AEs

Most common TEAEs are defined as any recorded TEAE corresponding to a PT with at least 5% of patients having at least one TEAE of this PT. Most common TEAEs will be derived overall and by age group and will be summarized by age group and for overall, by SOC and PT, in descending frequency according to incidence, starting from the most common event.

[Table 2-1](#) shows the identified and potential risks for LCZ696 and the specifically specified analyses for each risk. In addition, the following standard analyses will be applied to all risks.

- Numbers and percentages of patients with any TEAE within the risk category (or SOC/PT within risk category) by age group and risk category, SOC, PT and maximum severity.
- Exposure adjusted incidence rates per 100 patient-years for TEAEs within the risk category by age group and risk category.
- Listing of patient numbers per risk.

Table 2-3 Identified and potential risks

Risk	Analysis
Hyperkalemia	1. Standard analyses; 2. Numbers and percentages of patients with treatment emergent hyperkalemia among patients with/without hyperkalemia at baseline by age group and overall 3. Numbers and percentages of patients with any post-baseline serum potassium ≥ 5.5 mEq/L, >6.0 mEq/L and >6.5 mEq/L by age group and overall
Hypotension	1. Standard analyses;

Risk	Analysis
	
2. Blood pressures and change from baseline in blood pressures will be summarized by visit, time point, age group and overall using number of observations, mean, standard deviation, median, minimum, Q1, Q3, and maximum;
 
3. Numbers and percentages of patients with the following events during the treatment period will be provided by age group and overall:
 
• Post-baseline systolic blood pressure (SBP) < 5th percentile per age (Table 16-7 in the protocol);• At least 20 mmHg drop in SBP (post-baseline assessments comparing to baseline);• Simultaneous treatment emergent symptomatic hypotension and postbaseline SBP < 5th percentile per age (Table 16-7 in the protocol);• Simultaneous treatment emergent symptomatic hypotension and at least 20 mmHg drop in SBP (post-baseline assessments comparing to baseline);• Simultaneous post-baseline SBP < 5th percentile per age (Table 16-7 in the protocol) and at least 20 mmHg drop in SBP (post-baseline assessments comparing to baseline).
Angioedema (positively adjudicated events)	Standard analyses;
Renal impairment	
1. Standard analyses;
 
2. For serum creatinine and eGFR, the test values and changes from baseline will be summarized by visit, age group and overall using number of observations, mean, standard deviation, median, minimum, Q1, Q3, and maximum; the summaries will be provided for local and central lab separately;
 
3. Numbers and percentages of patients with the following events will be provided by age group and overall (the summaries will be provided for local and central lab together and if both central lab and local lab data are available, central lab result will take precedence over local lab result):
 
• eGFR decline by >25%, >40%, >50%, and/or >30 mL/min/1.73 m² (postbaseline assessments comparing to baseline) and <LLN;• eGFR < 45 mL/min/1.73 m² and/or eGFR < 30 mL/min/1.73 m²• Serum creatinine increase by >50% (post-baseline assessments comparing to baseline) and >ULN;• Serum creatinine increase by >0.5 mg/dL and >ULN (post-baseline assessments comparing to baseline),• serum creatinine post-baseline >2.0 mg/dL, >2.5 mg/dL, >3.0 mg/dL ;• Standard analyses within the subgroups additionally if possible: patients with baseline eGFR ≤170 mL/min/1.73 m² and >170 mL/min/1.73 m².

For safety topics of special interest defined in the CRS, the standard analyses will be performed.

